Appendix 2 Schedule of Pharmacokinetic and Pharmacodynamic Assessments

Visit	Timepoint	Sample Type
Cycle 1, Day 1	Prior to the dose	Plasma PK sample for cobimetinib + Plasma PD biomarker sample
	2 hr (\pm 30 min) after the dose	Plasma PK sample for cobimetinib
	4 hr (\pm 30 min) after the dose	Plasma PK sample for cobimetinib
	6 hr (\pm 30 min) after the dose	Plasma PK sample for cobimetinib
	24 hr (\pm 1 hr) after the dose, prior to dose on Day 2 of Cycle 1	Plasma PK sample for cobimetinib
Cycle 1, Day 21	Prior to the dose	Plasma PK sample for cobimetinib
	2 hr (\pm 30 min) after the dose	Plasma PK sample for cobimetinib
	4 hr (\pm 30 min) after the dose	Plasma PK sample for cobimetinib
	6 hr (\pm 30 min) after the dose	Plasma PK sample for cobimetinib
	24 hr (\pm 1 hr) after the dose	Plasma PK sample for cobimetinib
Cycle 2, Day 1	Prior to the dose (within 4 hr prior)	Plasma PK sample for cobimetinib
Cycle 2 (and every 2 cycles thereafter), Days 22–28	Samples should be collected on the day of scheduled tumor assessments.	Plasma PD biomarker sample
Study drug discontinuation	Any time during visit	Plasma PD biomarker sample

hr = hour; min = minute; PD = pharmacodynamics; PK = pharmacokinetic.

Note: Except for Day 1 of Cycle 1, all other study visits and assessments during the treatment period should be performed within 3 days of the scheduled date.

Appendix 3

Modified International Neuroblastoma Response Criteria

Below response assessment is modified from the original INRC publication in 1993.

DEFINITION OF MEASURABLE (EVALUABLE) DISEASE ON CT/MRI SCAN

The presence of at least one lesion that can be accurately measured in at least one dimension with the longest diameter at least 20 mm. With a spiral computed tomography (CT) scan, lesions must be at least 10 mm. The investigator will identify up to 10 measurable target lesions to be followed for response. Note that bone lesions will be considered as non-target lesions for evaluation of CT/magnetic resonance imaging (MRI) response since they will be evaluated with MIBG scans.

Malignant Lymph Nodes. To be considered pathologically enlarged and measurable, a lymph node must be ≥ 15 mm in the short axis when assessed by CT scan (CT scan slice thickness recommended to be ≤ 5 mm). At baseline and in follow-up, only the short axis will be measured and followed. Serial measurements of lesions are to be done with CT or MRI. The same method of assessment used to characterize each identified and reported lesion at baseline should be used during follow-up.

RESPONSE CRITERIA FOR MEASURABLE DISEASE ON CT/MRI SCAN

The sum of the longest diameter (LD) for all target lesions will be calculated and reported as the disease measurement. The response of the CT/MRI lesions will be defined as outlined below:

- Complete response (CR): Disappearance of all target and non-target CT/MRI lesions
- Very good partial response (VGPR): Greater than 90% decrease of the disease measurement for CT/MRI lesions, taking as reference the disease measurement done to confirm measurable disease at study entry; non-target CT/MRI lesions stable to smaller in size
- Partial response (PR): At least a 30% decrease in the disease measurement for CT/MRI lesions, taking as reference the disease measurement done to confirm measurable disease at study entry; non-target CT/MRI lesions stable to smaller in size
- Progressive disease (PD): At least a 20% increase in the disease measurement, taking as reference the smallest disease measurement since the treatment started, or a new site of tumor; non-target CT/MRI lesions stable, smaller, or increased in size
- Stable disease (SD): Neither sufficient shrinkage to qualify for PR nor sufficient increase to qualify for PD taking as reference the smallest disease measurement since the treatment started; no new sites of disease

Appendix 3

International Neuroblastoma Response Criteria (cont.)

RESPONSE CRITERIA FOR MORPHOLOGIC BONE MARROW DISEASE

Only those patients with morphologic evidence of neuroblastoma by routine H and E staining (neuron-specific enolase [NSE] staining only is not evaluable) will be evaluable to assess bone marrow response.

- CR: No tumor cells detectable by routine morphology on two subsequent bilateral bone marrow aspirates and biopsies done at least 3 weeks apart after study entry.
- PD: Tumor seen on morphology on two consecutive bone marrows done at least 3 weeks apart in patients who had no tumor in bone marrow at study entry

Patient may be declared to have PD in bone marrow after only one diagnostic bone marrow at the discretion of the treating physician

Patients who enter study with bone marrow tumor by morphology will be considered to have PD if there is a minimum of 25% tumor in the marrow by morphology and a doubling in the amount of tumor in the marrow compared with the level present at study entry. For example, a patient entering with 5% tumor in marrow by morphology must increase to >25% tumor to have PD; a patient entering with 30% tumor must increase to >60% tumor.

- SD: Persistence of an amount of tumor in the bone marrow by morphology that does not meet criteria for either CR or PD

Patients who clear morphologic tumor but have immunocytologic tumor will be called SD.

RESPONSE CRITERIA FOR MIBG-POSITIVE LESIONS

All patients with known MIBG-avid lesions will be evaluable for MIBG response following the first course of therapy. The following criteria will be used to report MIBG response:

- CR: Complete resolution of all MIBG-positive lesions
- PR: Resolution of at least one MIBG-positive lesion, with persistence of other MIBG positive lesions
- SD: No change in MIBG scan in number of positive lesions (includes patients who have same number of positive lesions but decreased intensity)
- PD: Development of new MIBG-positive lesions

Appendix 3

International Neuroblastoma Response Criteria (cont.)

DEFINITION OF OVERALL RESPONSE FOR EACH PATIENT WITH NEUROBLASTOMA

The International Neuroblastoma Response Criteria were developed to define responses in patients being treated with frontline therapy from diagnosis.¹ These criteria were utilized as a basis for the following response criteria, which integrate response at all sites defined as measurable in this study, including CT/MRI lesions that meet RECIST, MIBG-positive lesions, and bone marrow disease. These criteria will be used to define the overall response for each patient.

- CR: Disappearance of all target lesions; no evidence of tumor at any site (chest, abdomen, liver, bone, bone marrow, nodes, etc.); homovanillic acid (HVA) and vanillylmandelic acid (VMA) normal
- VGPR: Greater than 90% decrease of the disease measurement for CT/MRI target lesions, taking as reference the disease measurement done to confirm measurable disease in target lesions at study entry; all preexisting bone lesions with CR by MIBG; MIBG scan can be SD or CR in soft tissue lesions corresponding to lesions on CT/MRI; CR in bone marrow; no new sites of tumor; HVA/VMA normal
- PR: At least a 30% decrease in the disease measurement for CT/MRI target lesions, taking as reference the disease measurement done to confirm measurable disease in target lesions at study entry; bone marrow with CR; MIBG with either PR or CR in bone lesions; MIBG may be SD or CR in soft tissue lesions corresponding to lesions on CT/MRI; HVA/VMA may still be elevated.
- PD: Any one of the following:
 - At least a 20% increase in the disease measurement for CT/MRI target lesions, taking as reference the smallest disease measurement recorded since the start of treatment
 - Appearance of one or more new lesions or new sites of tumor
 - PD as defined above for either bone marrow or MIBG lesions
- SD: Stable disease by either CT/MRI lesion, bone marrow, or MIBG criteria; no new lesions; no new sites of disease

The overall response as assessed at any particular timepoint based on the various disease sites is summarized in the table below.

¹ Brodeur GM, Pritchard J, Berthold F, et al. Revisions of the international criteria for neuroblastoma diagnosis, staging, and response to treatment. *J Clin Oncol* 1993;11:1466–77.

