Response Evaluation Criteria in Solid Tumors: Modified Excerpt from Original Publication (cont.)

Evaluation of Non-Target Lesions

This section provides the definitions of the criteria used to determine the tumor response for the group of non-target lesions. While some non-target lesions may actually be measurable, they need not be measured and instead should be assessed only qualitatively at the timepoints specified in the protocol.

- CR: Disappearance of all non-target lesions and (if applicable) normalization of tumor marker level

All lymph nodes must be non-pathological in size (< 10 mm short axis).

- Non-CR/Non-PD: Persistence of one or more non-target lesions and/or (if applicable) maintenance of tumor marker level above the normal limits
- PD: Unequivocal progression of existing non-target lesions

The appearance of one or more new lesions is also considered progression.

Special Notes on Assessment of Progression of Non-Target Disease

When the Patient Also Has Measurable Disease. In this setting, to achieve unequivocal progression on the basis of the non-target disease, there must be an overall level of substantial worsening in non-target disease in a magnitude that, even in the presence of SD or PR in target disease, the overall tumor burden has increased sufficiently to merit discontinuation of therapy. A modest increase in the size of one or more non-target lesions is usually not sufficient to qualify for unequivocal progression status. The designation of overall progression solely on the basis of change in non-target disease in the face of SD or PR of target disease will therefore be extremely rare.

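### In neuroblastoma, Appendix 3 does not count growth of existing non-target or MIBG-positive lesions as progression, and its CT/MRI-level and overall partial-response texts disagree

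*Combined protocol and SAP*

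**What the plan says.** Sections 3.4.3, 6.5.1 and 6.5.2 make PFS a co-primary efficacy endpoint and DOR a secondary one. For neuroblastoma, progression is judged by the investigator under the modified INRC in Appendix 3.

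**CT/MRI.** The measurement covers target lesions only: "The sum of the longest diameter (LD) for all target lesions will be calculated and reported as the disease measurement". Progression is a rise of 20% or more in that sum over its lowest on-treatment value, "or a new site of tumor; non-target CT/MRI lesions stable, smaller, or increased in size". Stable disease is "Neither sufficient shrinkage to qualify for PR nor sufficient increase to qualify for PD". Partial and very good partial response at this level also require non-target lesions to be stable or smaller.

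**Bone.** On CT/MRI, "bone lesions will be considered as non-target lesions for evaluation of CT/magnetic resonance imaging (MRI) response since they will be evaluated with MIBG scans".

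**MIBG.** "PD: Development of new MIBG-positive lesions". Stable disease means an unchanged number of positive lesions.

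**Overall response.** Progression is any of a 20% rise in CT/MRI target lesions, new lesions or sites, or marrow or MIBG progression. The overall partial and very good partial response text sets no condition on non-target CT/MRI lesions.

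**Other tumors.** Appendix 6 (RECIST v1.1) includes "PD: Unequivocal progression of existing non-target lesions". Appendix 4 (RANO for high-grade glioma) counts clear progression of nonmeasurable disease.

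**The concern.** Disease that is visibly growing can be scored as stable. Because bone lesions are always non-target on CT/MRI, their growth is left to MIBG, and MIBG progression depends on new lesions. A patient followed only through such lesions has no progression route for growth of the disease present at entry, unless the marrow is involved.

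These patients are in the analysis. Section 4.1.1 admits disease evaluable by nuclear medicine, and Section 3.4.3 counts neuroblastoma patients with evaluable disease in ORR. Neuroblastoma PFS and DOR would omit a kind of progression that RECIST and RANO for high-grade glioma include, so events would tend to fall later.

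The second problem concerns response. Growth of non-target lesions blocks partial response in one part of Appendix 3 and is not mentioned in another, so the same patient can be a responder or not depending on which text is applied.

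**Working it through.** This is a matter of classification rules, and the plan states no figure to reproduce. The check sets the rules side by side and then passes test patients through them.

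| Growth of existing disease | Appendix 3 (neuroblastoma) | Appendix 6 (RECIST) | Appendix 4 (RANO, high-grade glioma) |
|---|---|---|---|
| Target or measurable lesions | PD at +20% from the smallest value | PD at +20% and at least 5 mm | PD at +25% in area |
| Non-target or nonmeasurable lesions | no PD rule | PD if unequivocal | PD if clear |
| MIBG-positive lesions, same number | no PD rule | not used | not used |
| Marrow, positive at entry | PD at 25% or more tumor with a doubling | not used | not used |

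**Test patients.** Assumption: marrow negative at entry is entered as CR in Appendix 3, Table 1.

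- **A.** Targets 0%, non-target lesions double, MIBG count stays at 5, marrow negative. Since 0% < 20% and nothing is new, CT/MRI is SD. MIBG is SD and marrow CR. Table 1 gives overall SD. Under Appendix 6 the same growth would be PD if judged unequivocal.
- **B.** Bone-only disease, 5 MIBG-positive lesions, all enlarge, still 5. There is no target sum, so the 20% test cannot be met. MIBG is SD on the count. The overall SD text applies.
- **C.** Targets −35%, non-target lesions grow, 1 of 5 MIBG-positive bone lesions resolves, marrow negative.
  - CT/MRI level: 35% ≥ 30%, but non-target lesions are not stable or smaller, so not PR. Shrinkage is sufficient for PR, so on the wording not SD. There is no 20% rise and no new site, so not PD. Table 1 then has no CT/MRI category to take in.
  - Overall text: target fall of at least 30%, marrow CR, MIBG PR in bone, catecholamines unrestricted. This is PR.
  - If CT/MRI SD is instead treated as whatever is left over, the triple SD / PR / CR has no row in Table 1, and the overall SD text gives SD. The patient is PR or SD according to the text used.
- **D.** Targets −35%, non-target stable, 1 of 5 MIBG-positive bone lesions resolves, the other 4 become more extensive, marrow negative. Overall PR.
- **Controls.** Targets +20%: PD. One new MIBG lesion: PD. Marrow 5% to 26%: PD. Marrow 30% to 61%: PD. Marrow 30% to 55%: SD. The marrow results agree with the worked examples in Appendix 3 (above 25% and above 60%).

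Patients A to D have no PFS event at that assessment.

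**Effect on ORR.** Table 6 in Section 6.1 requires 3 responders from a minimum of 10 neuroblastoma patients. At 10 patients one reclassification moves ORR by 1/10 = 10 percentage points. It decides expansion when the other patients supply exactly 2 responders: 2/10 = 20% fails, 3/10 = 30% passes.

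**The case against.** Several stronger readings are tempting, and the documents do not support them.

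- **That the quoted clause itself permits growth without progression.** It only describes what may accompany a progression already triggered by target growth or a new site. Deleting it would change no classification. The gap comes from the absence of any trigger for existing non-target or MIBG-positive disease.
- **That a patient can progress at every existing site unnoticed.** Marrow has its own rule. Death, new lesions and target growth remain events.
- **That each missed progression adds at least one scan interval** (8 weeks up to Cycle 12, later 16 and then 24). Section 4.5.5 allows an assessment whenever progression is suspected. Section 4.6.2 dates confirmed progression back to when it was first noted. Death or a new lesion may also come first. The delay can be zero.

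Other points for the plan carry weight. Appendix 6 itself expects progression on non-target disease alone to be extremely rare when target disease is stable or responding. Appendix 3 follows up to 10 target lesions against RECIST's five, so less soft-tissue disease is left unmeasured. Both confine the issue mainly to patients without measurable disease. Criteria differ by tumor type by design, Appendix 3 is a declared modification of a published system, no formal testing is planned, and expansion depends on responders, not PFS. These limit the consequences but do not tell an investigator how to score such a patient.

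Investigator judgment does not close the gap. Section 5.3.5.9 mentions symptomatic deterioration for rare cases, but within adverse event recording. It is in neither the PFS definition nor Appendix 3.

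**Conclusion.** The point holds and should be corrected. As written, unequivocal growth of existing non-target CT/MRI lesions or existing MIBG-positive lesions is not a PFS or DOR event in neuroblastoma. For non-target disease, RECIST and RANO for high-grade glioma count the equivalent growth. Any bias runs toward later events and applies mainly to patients with bone-only, MIBG-only or other non-measurable disease. Its size cannot be computed, because the documents give neither the share of such patients nor the rate of such progression.

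The partial-response mismatch is a separate internal inconsistency. Its effect on ORR is 10 percentage points per patient at a cohort of 10, and it can decide expansion only when that patient would be the third responder. The documents do not say how often this would happen.

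**What to change.** Revise Appendix 3 so that the CT/MRI, MIBG and overall definitions and Table 1 give one answer:

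1. State one explicit endpoint classification (PFS, DOR, ORR) for unequivocal growth of existing non-target CT/MRI lesions, and one for unequivocal growth of existing MIBG-positive lesions, consistent with how progression is counted in the other cohorts.
2. Carry the condition that non-target lesions be stable or smaller into the overall partial and very good partial response text, so that it matches the CT/MRI level.
3. Check that every combination of site results has a row in Table 1.

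Section 4.6.2 uses the same criteria for stopping study drug, so the sponsor must reconcile it with the revised appendix. How treatment should follow is for the sponsor to settle and is not proposed here.

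The cost is a short text edit, with no scans beyond those already scheduled. The downside is some earlier PFS events and possibly a slightly lower ORR in neuroblastoma.

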Appendix 3 International Neuroblastoma Response Criteria (cont.)

Table 1 Overall Response at Any Timepoint

CT/MRI Lesions	MIBG Lesions	Bone Marrow	Catechols	Overall Response
PD	Any	Any	Any	PD
Any	PD	Any	Any	PD
Any	Any	PD	Any	PD
CR	CR	CR	Normal	CR
VGPR	CR in bone lesions ; May have SD/CR in soft tissue sites corresponding to lesions on CT/MRI	CR	Normal	VGPR
PR	PR/CR in bone lesions; May have SD/CR in soft tissue sites corresponding to lesions on CT/MRI	CR	Any	PR
SD	SD	SD	Any	SD
SD/PR/VGPR/CR	SD	SD/CR	Any	SD
SD/PR/VGPR/CR	SD/PR/CR	SD	Any	SD

CR=complete response; CT=computed tomography; MIBG=metaiodobenzylguanidine; MRI=magnetic resonance imaging; PD=progressive disease; PR=partial response; SD=stable disease; VGPR=very good partial response.

Appendix 4

Response Assessment in Neuro-Oncology Criteria for High-Grade Glioma

Response	Criteria
Complete response	
Requires all of the following:
 
 • Complete disappearance of all enhancing measurable and nonmeasurable disease sustained for at least 4 weeks • No new lesions • Stable or improved non-enhancing (T2/FLAIR) lesions • Patients must be off corticosteroids (or on physiological replacement doses only) • Clinical status is stable or improved
Partial response	
Requires all of the following:
 
 • $\geq 50\%$ decrease compared with baseline in the sum of products of perpendicular diameters of all measurable enhancing lesions sustained for at least 4 weeks • No progression of nonmeasurable T1 enhancing disease • No new lesions • Stable or improved non-enhancing (T2/FLAIR) lesions on the same or lower dose of corticosteroids compared to baseline • Clinical status is stable or improved 
Note: Patients with nonmeasurable disease only cannot have a partial response; the best response possible is stable disease

Stable disease	
Requires all of the following:
 
 • Patient does not qualify for complete response, partial response, or progression • Stable non-enhancing (T2/FLAIR) lesions on same or lower dose of corticosteroids compared to baseline • Clinical status is stable or improved 
Note: In the event that the corticosteroid dose was increased for new symptoms and signs without confirmation of disease progression on neuroimaging, and subsequent follow-up imaging shows that this increase in corticosteroids was required because of disease progression, the last scan considered to show stable disease will be the scan obtained when the corticosteroid dose was equivalent to the baseline dose.

Appendix 4 Response Assessment in Neuro-Oncology Criteria for High-Grade Glioma (cont.)

Response	Criteria
Progression	
Defined by any of the following:
 
 • $\geq 25\%$ increase in sum of the products of perpendicular diameters of enhancing lesions compared with the smallest tumor measurement obtained either at baseline (of no decrease) or best response, on a stable or increasing dose of corticosteroids • Significant increase in T2/FLAIR non-enhancing lesions on stable or increasing doses of steroids compared with baseline scan or best response after initiation of therapy, not caused by comorbid events (e.g., radiation therapy, demyelination, ischemic injury, seizures, postoperative changes, or other treatment effects) • Presence of any new lesions • Clear clinical deterioration not attributable to other causes apart from the tumor (e.g., seizures, medication adverse effects, complications of therapy, cerebrovascular events, infection, and so on) or decreases in corticosteroid dose • Failure to return for evaluation due to death or deteriorating condition • Clear progression of nonmeasurable disease

FLAIR = fluid-attenuated inversion recovery.

Note: Adapted from Wen PY, Macdonald DR, Reardon DA, et al. Updated response assessment criteria for high-grade gliomas: Response assessment in neuro-oncology working group. *J Clin Oncol* 2012;28:1963–72.

Appendix 5

Response Assessment in Neuro-Oncology Criteria for Low-Grade Glioma

Response	Criteria
Complete response	
Requires all of the following criteria compared with the baseline scan:
 
 • Complete disappearance of the lesion on T2 or FLAIR imaging (if enhancement had been present, it must have resolved completely) • No new lesions, no new T2 or FLAIR abnormalities apart from those consistent with radiation effects, and no new or increased enhancement • Patients must be off corticosteroids or only on physiological replacement doses • Patients should be stable or improved clinically
Partial response	
Requires all of the following criteria compared with the baseline scan:
 
 • $\geq 50\%$ decrease in the product of perpendicular diameters of the lesion on T2 or FLAIR imaging sustained for at least 4 weeks compared with baseline • No new lesions, no new T2 or FLAIR abnormalities apart from those consistent with radiation effects, and no new or increased enhancement • Patients should be on a corticosteroid dose that should not be greater than the dose at time of baseline scan and should be stable or improved clinically
Minor response	
Requires the following criteria compared with baseline:
 
 • A decrease of the area of non-enhancing lesion on T2 or FLAIR magnetic resonance imaging between 25% and 50% compared with baseline • No new lesions, no new T2 or FLAIR abnormalities apart from those consistent with radiation effect, and no new or increased enhancement • Patients should be on a corticosteroid dose that should not be greater than the dose at time of baseline scan and should be stable or improved clinically
Stable disease	
Is present if the changes do not qualify for complete, partial, or minor response, or progression and requires:
 
 • Stable area of non-enhancing abnormalities on T2 or FLAIR imaging • No new lesions, no new T2 or FLAIR abnormalities apart from those consistent with radiation effect, and no new or increased enhancement • Patients should be on a corticosteroid dose that should not be greater than the dose at time of baseline scan and should be stable or improved clinically

